SDT constructs	TSRQ Autonomous Self-Motivation (α .81-.84)(Appx.8) ^{97,122} Perceived Competence Scale (MASES-R) (.92, test-retest [3 mos.] .51) (Appx.7). ^{101,123,124}	Baseline,3,6,12,18 mos
Exploratory Outcomes		
Cost effectiveness	Costs of additional personnel time, SMASH devices, ED visits, unplanned outpatient visits & hospitalizations, workdays lost.	First 6 mos of trial & through post-trial follow-ups
Physical Risk Factors	TC, LDL, HgA1c, blood glucose from FQHC standard care via MedCorp (intra-assay variations all <5%; inter-assay variations 3.3% to 6.6%)	Baseline,6,12,18 mos
Potential MA Mediators	HTN Knowledge (.70) (Appx.9); ^{129,130} Short Test of Functional Health Literacy (S-TOFHLA)(.68) (Appx.10); ¹³¹⁻¹³³ SF-8(α .87) (Appx.12); ¹³⁵ Med Side effects (Appx.11); ¹³⁴ Adverse events; Pittsburgh Sleep Quality Index (sleep quality) (.83; test-retest [1mo, 12 mo] .85, .68) (Appx.16); ^{138,139} Beck Depression Inventory (BDI) (0.82-0.92); (Appx.13); ¹¹³⁻¹¹⁵ Perceived Stress Scale (PSS) (.84-.86; test-retest [2 day] .85)(Appx.15); ^{136,137} Illness Perception Questionnaire (IPQ-R; perceived disease severity); .84, test-retest [3 weeks,6 mos] .74.,.74) (Appx.17); ¹⁴⁰ Questionnaire on Quality of Patient & Physician Interaction (QQPPI)(Appx.18). ¹⁴¹	Baseline,3,6,12,18 mos
Values/Beliefs/Goals	Values, Beliefs, Goals (test-retest [1 mo].85) (Appx.14). ¹⁰⁶	Baseline,3,6,12,18 mos
Anthropometrics	Ht./Wt./Girth (Appx.6).	
Sociodemographics	Age, education level, income, type of healthcare insurance	Baseline
Feasibility	Recruitment and Retention rates.	End of trial
System Usability	System Usability Scale (Appx. 19); ^{146,147} Patient/Provider SMASH/SC Treatment Satisfaction & Usability Scale (TSUQ) (α .82-.96, test-retest [1wk] .98) (Appx.20); ^{144,145} User Version of Mobile App Rating Scale (uMARS) (.90, test-retest [2, 3 mos] .66, .70) (Appx.21). ^{142,143}	At 6 mos (All subjects) After all subjects complete 6 mos trial (Providers)
Process/uptake	Patient level (e.g., connection/reloads of MedMinder, BP uploads via phone & opening of messages /education info) & provider level (e.g., opening of patient summary reports & phone alerts).	First 6 mos of trial

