Exploratory Moderator Analyses: Our conceptual model will guide moderator analyses of MA and BP control using logistic regression with >90% MA or BP control at 6 months as dependent variable and the GLMM/GEE model over the entire study (measurement times 3, 6, 12 and 18 months). Modeling will be carried out in a sequential fashion. Initial set of models will first be adjusted for sociodemographics (age, gender, education, marital status, income), autonomous motivation and biobehavioral factors (e.g., stress, sleep quality, depressive symptoms, med side effects, etc.). If needed, models will be further adjusted for new comorbidities (e.g., diabetes) and associated additional meds. Effect modifications of covariates (moderators) will be examined through inclusion of a covariate-by-group (SMASH vs SC) interaction term in the multivariable models.⁶⁷ We are especially interested in the interaction of treatment by gender, as well as SES and autonomous motivation.

Exploratory MNA Mediation Analyses: Potential mediators will be examined individually and subsequently in a multivariable model. Exploratory analyses will follow modifications suggested by MacKinnon, Fairchild and Fritz¹⁵⁷ of the causal steps approach developed by Baron & Kenny.¹⁵⁸ Analyses will be guided by our conceptual model framed upon change scores in SDT constructs (competence & autonomous motivation) followed by MNA mediators identified in the empirical literature including biobehavioral (e.g. stress, med side effects, depression symptoms, sleep quality, perceived disease severity, doctor-patient relationship, quality of life, HTN knowledge/beliefs) and process /uptake features (e.g., opening of motivational/reinforcement messages/education info, BP graph uploads via phone, patient SMASH (or SC) usability and satisfaction scale

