Description: (The purpose of TSRQ is to assess the degree to which one's motivation for a particular behavior or set of behaviors is relatively autonomous or self-determined, (of if motivation is externally driven (controlled)). The responses on the autonomous items are averaged to form the reflection of autonomous motivation for the target behavior and the responses on the controlled items are averaged to form the reflection of controlled motivation for the target behavior. (In those studies where a motivation has also been assessed, the amotivated responses are also averaged. These three subscale scores can be used separately, or a Relative Autonomy Index can be formed by subtracting the average for the controlled reasons with the average for the autonomous reasons. (Autonomous: (1, 3, 6, 8, 11, 13) (Controlled: (2, 4, 7, 9, 12, 14) (No motivation: (5, 10, 15))

(

((

(

1. Source: (Williams GC et al. (1996) Motivational predictors of weight loss and weight loss maintenance, Journal of Personality and Social Psychology, (70), (115) 26.

(

Sample Characteristics: (94 obese individuals who enrolled in a weight loss program. ((27% male (Mean age 43.4 (Range: (20-77))

(

Psychometric Properties: (Reliability: (Test Retest (coefficient (after 18 months (or more) (Autonomous items: $r = .47$ ($p < .01$), (Controlled items: $.34$ ($p < .05$)).
Validity: (Autonomous items correlated with Autonomy orientation score of General Causality Orientations Scale ($r = .38$, $p < .001$) and the Perceived Autonomy Support of the Health Care Climate Questionnaire ($r = .38$, $p < .001$).
Predictive Value: (Autonomous items at start predicted attendance ($r = .34$, $p < .001$) and BMI ($r = .11$, $p < .05$)).

(

2. Source: (Williams GC et al. (1998) Autonomous regulation and long term medication adherence in adult outpatients, Health Psychology, (17), (269) 276.

(

Sample Characteristics: (126 Adults taking at least one prescription pill ((24.6% male, (mean age 56.3 years, (range: (37-85))

Psychometric Properties: (Reliability: (Internal consistency: (Cronbach's alpha score, (Autonomous items = $.81$, (Controlled items = $.84$)
Validity: (Autonomous items correlated with the Perceived Autonomy Support of the Health Care Climate Questionnaire ($r = .24$, $p < .05$).
Predictive Value: (Autonomous items predicted adherence ($r = .58$, $p < .0005$)).

(

(

Medication Adherence (ASRQ)

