Somewhat
True

3

4

5

True

6

7

Very True

9. ~~Because I feel pressure from others to do so.~~

1

Not at all
True

2

Somewhat
True

3

4

5

True

6

7

Very True

10. ~~Because it is easier to do what I am told than to think about it.~~

1

Not at all
True

2

Somewhat
True

3

4

5

True

6

7

Very True

11. ~~Because it is consistent with my life goals.~~

1

Not at all
True

2

Somewhat
True

3

4

5

True

6

7

Very True

12. ~~Because I want others to approve of me.~~

1

Not at all
True

2

Somewhat
True

3

4

5

True

6

7

Very True

13. ~~Because it is very important for being as healthy as possible.~~

1

Not at all
True

2

Somewhat
True

3

4

5

True

6

7

Very True

14. ~~Because I want others to see I can do it.~~

1

Not at all
True

2

Somewhat
True

3

4

5

True

6

7

Very True

15. ~~don't really know why.~~

1

Not at all
True

2

+

3

Somewhat
True

4

+

5

True

6

7

Very True

+

Medication Adherence Self Efficacy Scale Revised (MASESR) (Fernandez, et al., (2008)

Description: (The Medication Adherence Self Efficacy Scale (MASESR) consists of 13 self-administered questions, which measure situation-specific efficacy beliefs regarding adherence to prescribed antihypertensive medications. Responses are Not at all sure (=1, A little sure (=2, Fairly sure (=3, Extremely sure (=4. ((

1. (Fernandez(S, et al. ((2008) (Revision and validation of the medication adherence self efficacy scale (MASES) in hypertensive African Americans. Journal of Behavioral Medicine, 31(6), 453-462
Sample Characteristics: ((168 hypertensive African Americans ((14% (male) (mean age 54 ((±12.4) (years. ((

+ Psychometric Properties: ((Reliability: (Chronbach's alpha (= .92 (Test-Retest ((3 months) (coefficient (= .51 ((p < .001). ((
Concurrent Validity: (With self-report of adherence, (Non-adherent (Mean (= 3.51 (±.52, (adherent (Mean (= 3.81 (±.33 ((p < .001) ((
With electronic adherence measure (MEMS) at 3 months: (r (= .20, (p (= .02. ((
Predictive validity: (Baseline MASESR (with MEMS) at 3 months: (r (= .19, (p (= .02. ((

2. (Voils(C, et al., ((2012) (Initial Validation of a Self-Report Measure of the Extent of and Reasons for Medication Nonadherence. Med Care, 50, 1013-1019. ((
Sample Characteristics: ((202 hypertensive veterans ((86% (male), (mean age 64.1 ((±11) (years, (50% (Black. ((

(Psychometric Properties: ((Concurrent validity: (with Extent of Nonadherence measure: (r (= .42, (p < .0001. ((

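### Mediation is framed on change scores with no stated baseline-mediator covariate, which can strongly attenuate the mediator-to-adherence path

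*Combined protocol and SAP*

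**What the plan says.** In the combined protocol and SAP, the D.10 paragraph on exploratory mediation says: "Analyses will be guided by our conceptual model framed upon change scores in SDT constructs (competence & autonomous motivation". Its results feed an exploratory structural equation model whose findings are to guide refinement of SMASH for a later effectiveness trial. The Introduction to the Revised Application names these two constructs as the main adherence mediators.

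On covariates, the Aim 1 text of D.10 adjusts for the baseline of the dependent variable. In the mediator-to-adherence model the mediator is a predictor, so that rule does not bring in its baseline. The moderator paragraph lists autonomous motivation as an adjustment variable, with no time point. It does not name competence, and the mediation paragraph does not refer to it.

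Table 3 lists the competence measure as "Perceived Competence Scale (MASES-R) (.92, test-retest [3 mos.] .51) (Appx.7", taken at baseline and months 3, 6, 12 and 18. The MASES-R appendix gives three correlations from a validation sample of 168:
- retest: "Test-Retest ((3 months) (coefficient (= .51 ((p < .001"
- 3-month score with adherence: "With electronic adherence measure (MEMS) at 3 months: (r (= .20, (p (= .02"
- baseline score with the same adherence: "Predictive validity: (Baseline MASESR (with MEMS) at 3 months: (r (= .19, (p (= .02"

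**The concern.** A change score used alone as predictor assumes that one point more at follow-up and one point less at baseline mean the same for adherence. If people who start with higher competence also tend to adhere better later, that assumption is wrong. Subtracting the baseline then removes part of the signal that the follow-up score carries. The appended correlations show this pattern: baseline and follow-up competence relate almost equally to later adherence, so their difference relates to it hardly at all.

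At stake is the reading of the mediation results. They are meant to identify the active ingredients of SMASH, and a path shrunk by the choice of score could be taken as evidence that competence matters less than it does.

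**Working it through.** The plan gives no power, effect size or change-score correlation for mediation, so there is no figure of its own to reproduce.

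**Inputs (MASES-R appendix).** Retest r = .51; follow-up score with adherence r3 = .20; baseline score with adherence r0 = .19; n = 168. Whole-sample SDs are not given, so equal SDs are assumed.

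**Change alone.**
- Correlation with adherence: (r3 - r0)/sqrt(2(1 - r)) = .01/sqrt(.98) = .010.
- Standardised slope: (r3 - r0)/(2(1 - r)) = .01/.98 = .010.

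**Follow-up score adjusted for baseline.**
- Follow-up slope: b3 = (r3 - r·r0)/(1 - r²) = (.20 - .0969)/.7399 = .139.
- Baseline slope: b0 = (r0 - r·r3)/(1 - r²) = (.19 - .102)/.7399 = .119.
- Partial r of follow-up given baseline: .1031/sqrt(.9639 × .7399) = .122.

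**Why they differ.** Write adherence as b3·M3 + b0·M0 = b3·(M3 - M0) + (b3 + b0)·M0. With M0 in the model, the coefficient on change is exactly b3. With M0 left out and equal SDs, it becomes (b3 - b0)/2 = (.139 - .119)/2 = .010. The two agree only when b0 = -b3, that is, when adherence depends on change and nothing else.

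**Uncertainty of the .010.**
- Rounding of the inputs: .00 to .02.
- Ratio of follow-up to baseline SD from 0.8 to 1.25: -.03 to +.05.
- Sampling error, Fisher z at n = 168: -.14 to +.16. The interval for the partial r is -.03 to +.27, so the two overlap widely.
- At n = 168, correlations of .20 and .19 give p = .009 and .014. The reported .02 for both fits about 140 to 147 people with electronic data. At n = 134 the interval for change would be -.16 to +.18.

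**Consequence under three true models.** Simulation of 4,000 trials, N = 192, retest .51, a 0.5 SD arm effect on competence (assumed), continuous adherence, no clustering. Power is for both paths significant at two-sided .05. Slopes come from the formula above.

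| True model for adherence | Slope, change alone | Slope, adjusted | Power, change alone | Power, adjusted |
|---|---|---|---|---|
| Appended correlations (.139·M3 + .119·M0) | .010 | .139 | 5% | 38% |
| Follow-up level only (.30·M3) | .15 | .30 | 51% | 94% |
| Change only (.30·(M3 - M0)) | .30 | .30 | 93% | 94% |

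At N = 176 the first row is about 5% against 35%. With an arm effect of 0.8 SD it is about 5% against 39% at N = 192 and 6% against 37% at N = 176.

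**The case against.** The strongest reply is that D.10 describes a conceptual framework and not a regression equation. It does not say that baseline is left out, and if baseline is a covariate, change and follow-up scores give the same slope. That stands. The gap is that the covariate is unstated, and the natural reading of the text does not supply it.

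Second, the .01 does not carry over. It relates change in competence to the level of adherence, in a sample for which the appendix reports no intervention. The trial enrols nonadherent patients and tries to raise competence. The association needed there cannot be derived from three correlations, and the interval is wide. This also stands, which is why the figure serves only as illustration.

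Third, the arm-to-mediator path may already be handled. Both constructs are Aim 2 outcomes, and D.10 says Aim 2 modelling follows the Aim 1 approach, which adjusts for baseline of the dependent variable. So the documents do not show that this path is unadjusted.

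A reader might go further and infer that mediation by competence would be missed even if real. The documents do not support that. The 5% power holds only if the appended correlations apply to the trial, and if adherence depends on change itself, almost nothing is lost. Nor can a comparable calculation be made for autonomous motivation. The TSRQ appendix takes its retest and adherence correlations from different studies and gives no pair of baseline and follow-up correlations with adherence.

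Finally, the analysis is exploratory, and refinement also draws on focus groups and usability data. That lowers the stakes but is no reason to keep the weaker form.

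**Conclusion.** The point holds as a free improvement to an exploratory analysis. As written, D.10 allows a mediator-to-adherence model on change alone, which can attenuate that path strongly. On the appended MASES-R figures with equal SDs, the slope is .010 instead of .139. The size of the loss in the trial is unknown, since it depends on how far baseline competence predicts adherence beyond change.

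The recommendation does not rest on the .01. The adjusted model contains the change-score model as a special case, and in the three settings tried it did as well or much better. These results assume linear relations, no clustering and no unmeasured confounding of mediator and adherence.

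Adjustment removes the attenuation but does not make the analysis well powered for a small mediated effect. No primary or secondary test is affected.

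**What to change.** In the D.10 mediation paragraph, state that each questionnaire mediator with a baseline measurement enters as its follow-up score with its own baseline score as a covariate (equivalently, the change score plus the baseline score). Apply this in both mediation paths, the multivariable mediator model and the structural equation model. The same sentence can say whether baseline adherence is also a covariate. Uptake measures and the month-6 usability and satisfaction scales have no baseline and are not affected.

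The cost is SAP wording and one degree of freedom per mediator. Table 3 already schedules the baseline scores, so no visit or instrument is added. A null mediation result should still be reported with its interval and a note on limited power.
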